1.2 Secondary Objective(s)

- To describe the association of major financial hardships with mCRC treatment by demographic factors, including age, race, marital status, employment status, and income.
- b. To explore whether occurrence of major financial hardship is associated with poorer health-related quality of life over time.
- c. To profile the magnitude and timing of treatment-related changes in patients' income, assets, debt, and employment, and to quantify major out-of-pocket expenses during the 12 months following registration.
- d. To explore the extent to which health insurance factors (e.g. high copayments, deductibles, premiums, loss/change of insurance plan) are associated with major financial hardship and treatment non-adherence.
- e. To determine feasibility of recruiting primary caregivers and measuring caregiver burden and caregivers' perceptions about cancer treatment costs.
- f. To determine the feasibility of conducting a prospective-multi-site longitudinal cohort study assessing financial outcomes in patients with mCRC undergoing treatment within the NCORP network.

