7.0 STATISTICAL CONSIDERATIONS

7.1 Primary Objective

The primary objective is to estimate the incidence of treatment-related major financial hardship (debt, selling/refinancing home, borrowing money from friends/family, ≥ 20% income decline) among evaluable patients with newly diagnosed metastatic colorectal cancer (mCRC) treated at NCORP sites.

Given serial measurements, the primary endpoint is time to first evidence of major financial hardship. Dropout due to death from mCRC will be a significant factor in this study. Recent randomized clinical trial data have reported 1-year survival of around 60% for this population. (19) Therefore death represents a substantial competing risk in the detection of financial hardship, which is accounted for in the study design. Both time to first evidence of major financial hardship and death are assumed to exhibit exponential decline. Dropout for reasons other than death (e.g. transferring care to another institution, withdrawal of consent) following enrollment in the study is estimated to be around 10% based on other studies in the literature. (20,21) Non-death related dropouts will be censored.

Based on preliminary data, we anticipate that 40% of patients will experience major financial hardship at some point in the first year after diagnosis. Estimates of major financial hardship at 1 year will be derived using cumulative incidence to account for competing risks.

Under this scenario, a sample size of n=320 eligible, evaluable patients will allow us to estimate the confidence interval to within \pm 8% (based on the upper bound of the 95% confidence interval using an exact binomial in patients with complete follow-up), if the assumed incidence is at least 40%. Thus this sample size will allow us to estimate the confidence interval to within \pm 20% of the assumed incidence (the "relative accuracy"). The relative accuracy will improve with higher incidence as shown in the table below. This estimate is conservative as it is based on the assumption of no information from the 50% of patients estimated to drop out.

| Assumed incidence (p) | 95% confidence interval about p | Confidence range | Relative accuracy [(95% CI upper bound – p)/p] |
|-----------------------|---------------------------------|------------------|--|
| 20% | 14.1% - 27.0% | ± 7.0% | ± 35.2% |
| 30% | 23.0% - 37.7% | ± 7.7% | ± 25.8% |
| 40% | 32.3% - 48.0% | ± 8.0% | ± 20.1% |
| 50% | 42.0% - 58.0% | ± 8.0% | ± 16.0% |

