The feasibility of successfully accruing to a prospective-multi-site longitudinal cohort study assessing financial outcomes in patients with metastatic colorectal cancer (mCRC) undergoing treatment within the NCORP network will be examined. The total anticipated accrual time is 3 years. To be conducted in that timeframe, each of the NCORP components (we anticipate 25 NCORP components) will each need to enroll, on average, about 5 patients per year. Accrual will be monitored regularly. Given the open eligibility criteria, we hypothesize that enrollment will be feasible. However accrual will be assessed at 1.5 years after study activation. If monthly average accrual in quarters 5-6 after study registration is < 50% of projected accrual, efforts will be made to increase accrual over the succeeding 6 month period. If after 2 years, monthly accrual remains < 50% of projected accrual, study revision will be considered. In order to address the potential for selection bias, we will compare demographics (age, race, gender, etc.) of the final cohort to the typical patient population seen at the various practice sites.

The feasibility of incorporating a caregiver component to the study will also be examined. Caregiver participation is optional. The caregiver component will be considered feasible if the designated caregivers for > 50% of eligible patients complete and submit their baseline and at least one follow-up assessment. We will use means, medians, proportions to describe the participating caregiver population. Our analyses will be largely descriptive. We will look at the proportion of caregivers who experienced changes in employment and expenses (caregiver questionnaire items 11 and 13). We expect that caregivers of patients who experience financial hardship will be more likely to report financial burden. We will therefore investigate the association between patient-reported financial hardship and level of caregiver-reported financial burden. We will compare proportion of caregivers experiencing 'high financial burden' (≥ 3 on Likert scale) for patients who do vs. do not report major financial hardship using two-sample t tests. If our caregiver accrual is very poor (<20%), we will focus on describing the patient population rather than attempting to correlate caregiver and patient responses.

7.3 Other Secondary Endpoints:

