The linkage of clinical and financial data with credit histories obtained from TransUnion will allow us to explore additional indicators of financial stress, including high balances

and past due amounts of credit card and bankcards as well as evidence of bankruptcies, liens, and collections or repossessions. These data will also allow us to corroborate self-reports of debt and bankruptcy in order to investigate the reliability of self-reports in estimating financial hardship. Credit reports will be obtained at baseline and at 6 and 12 months after registration. Given the poor 1-year survival for this patient cohort (60%), multiple post-baseline credit reports are requested to limit bias due to missing data related to death.

Other secondary objectives including measurement of out-of-pocket expenses, health insurance changes, changes in assets/income/wealth, measurement of debt and spending by credit report histories, and assessment of patient, caregiver, and bereaved caregiver financial stress will be handled using descriptive statistics (e.g. mean, median, proportions). We will use descriptive statistics to summarize baseline patient characteristics and will compare populations using two-sample means and proportions tests (α level 0.05). Caregiver strain index will be scored based on responses (score range 0 to 26). Mean scores will be compared for caregivers of patients reporting vs. not reporting at least one financial hardship.

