10.2 Administration of Questionnaires to Caregivers

- a. Caregivers will be asked to fill out the S1417CD Caregiver Questionnaire at baseline (following consent), and subsequently at 6 and 12 months following patient registration. The questionnaire will be self-administered and is anticipated to require a total of 30 minutes to complete at each study time point, by phone or by mail. The caregiver should be asked to complete the Caregiver Questionnaire even if the patient does not complete the patient questionnaires at the time point. Upon patient death, the caregiver's participation will discontinue and no further Caregiver Questionnaires are required.
- b. It is preferable for the caregiver to complete the Caregiver Questionnaire during the patient's routine clinical visits coinciding with the appropriate study time point; however, the study staff should defer to the caregiver's preferences for completing the questionnaires. Questionnaires may be done at home and mailed back to the research staff. Target follow-up assessments should be based on the date of patient registration. A window of ± 21 days is allowed for each assessment to provide more flexibility in scheduling.
- c. If the caregiver prefers to mail it back, the research site will provide a preaddressed stamped envelope. If the caregiver prefers to answer the questionnaire over the phone, research staff will make arrangements for a phone interview. When responses are obtained via phone interview, it is important that the caregiver is looking at a copy of the questionnaire while the staff conducts the interview. The date of the telephone interview is to be recorded on the Caregiver Questionnaire.
- d. It is very important to review the completed questionnaire with the caregiver during the clinic visit or over the phone to be sure all of the questions have been answered and, when the caregiver is directed to mark only one response, that

only one answer is marked. If the caregiver has marked more than one answer per question, ask them which answer reflects how he/she is feeling. If the caregiver has skipped a question, bring it to their attention and ask if they would like to answer the question. If the caregiver does not want to answer a particular question, the CRA will enter "Not answered by the caregiver" in Medidata $RAVE^{\otimes}$.

- 10.3 Criteria for Removal for Consented Caregiver from Study Participation
 - a. Caregiver completes 12 months of study participation.

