 - b. Patient death.
 - c. Patient removed from protocol participation (see Section 4.7).
 - d. The caregiver may withdraw from the study at any time for any reason. The patient will continue participation even if the consented caregiver discontinues study participation.
 - NOTE: If the patient is alive cannot or refuses to complete questionnaires at a study time point, but remains on protocol, the caregiver will continue to complete the Caregiver Questionnaire at the study time points.
 - e. If the Caregiver Questionnaire is not completed at a time point, document the reason on the S1417CD Cover Sheet for Patient and Caregiver-Completed Questionnaires for that time point. If the caregiver discontinues study participation prior to 12 months, document the reason on all cover sheet submissions for the remaining time points the patient continues study participation.

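### Does the >50% caregiver feasibility rule in 7.2 need an allowance for early patient deaths, and does the bereaved-caregiver item in 7.3 leave a gap that must be filled?

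*Combined protocol and SAP*

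**What the plan says.** Objective 1.2e is "To determine feasibility of recruiting primary caregivers and measuring caregiver burden", together with caregivers' perceptions of treatment cost. Section 7.2 (Feasibility) sets one criterion for it: the component is "feasible if the designated caregivers for > 50% of eligible patients complete and submit their baseline and at least one follow-up assessment". The same paragraph makes participation optional, describes the caregiver analyses as largely descriptive, and gives one caregiver trigger with a consequence: "If our caregiver accrual is very poor (<20%), we will focus on describing the patient population".

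Section 10.2a schedules the caregiver form "at baseline (following consent), and subsequently at 6 and 12 months following patient registration", and 10.2b allows 21 days either side. On patient death, the caregiver's "participation will discontinue and no further Caregiver Questionnaires are required". Section 10.3 repeats this (10.3b) and adds removal of the patient from protocol as a further reason for the caregiver to stop (10.3c). Under 10.1e a caregiver who stops cannot be replaced.

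On mortality, section 7.1 says: "Recent randomized clinical trial data have reported 1-year survival of around 60% for this population". It assumes exponential decline and adds about 10% dropout for reasons other than death.

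Section 7.3 says that "assessment of patient, caregiver, and bereaved caregiver financial stress will be handled using descriptive statistics". Neither the calendar in 5.0 nor the submission schedule in 9.4 has a form for a caregiver after the patient's death.

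**The concern.** The criterion divides by all eligible patients but needs a form that cannot exist until nearly six months after registration. In a population with 40% one-year mortality, a sizeable share of the denominator can never succeed, and 7.2 does not say so. One percentage then merges three things: the patient died early, no caregiver consented, or an enrolled caregiver did not return forms. A planner of a later study would respond differently to each. The worry is that a failed criterion would be read as caregivers being unwilling when the cause was patient mortality.

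The 7.3 item looks like a second gap, because it lists a description for a group from whom no data are collected.

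**Working it through.** **Inputs.** One-year survival 60%, exponential (7.1); death hazard 0.51 (7.2); non-death dropout about 10% (7.1); first caregiver follow-up at month 6 ± 21 days (10.2); 374 enrolled, 5% ineligible, 10% without baseline forms (7.1). The plan gives no expected caregiver completion rate, so the rates below are assumptions.

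**Plan's own figures.** Hazard = −ln(0.60) = 0.511, stated as 0.51. Enrolment = 320/(0.95 × 0.90) = 374.3, stated as 374. Both reproduce.

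**Share who can still succeed.** With S(t) = 0.60^t:
- Month 6: 0.60^0.5 = 0.7746.
- Window opening, t = 0.5 − 21/365.25 = 0.4425 years: 0.60^0.4425 = 0.7977.

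The month-12 form also counts as a follow-up, but reaching it requires surviving past month 6, so the month-6 window is the binding point.

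**What the rule means among living patients.** 0.50/S(t):
- Month 6: 0.50/0.7746 = 64.5%.
- Window opening: 0.50/0.7977 = 62.7%.

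**Adding dropout.** Assume the 10% accrues at a constant rate over the year and always ends caregiver participation:
- Month 6: 0.7746 × 0.9^0.5 = 0.735, so the bar is 0.50/0.735 = 68.0%.
- Window opening: 0.7977 × 0.9^0.4425 = 0.761, so the bar is 0.50/0.761 = 65.7%.

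The most the rule could ever show is therefore about 77-80% counting deaths only, or about 73-76% with dropout. Both are well above 50%.

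**Sensitivity to survival** (month 6, deaths only): at 70% one-year survival, 0.50/0.70^0.5 = 59.8%; at 80%, 0.50/0.80^0.5 = 55.9%. The reference behind the 60% is, by its title in 12.0, a trial in previously treated disease, whereas 3.1a enrols newly diagnosed metastatic patients. The plan's figure may therefore overstate early deaths.

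**Chance of meeting the rule.** Eligible n = 374 × 0.95 = 355, so 178 successes are needed. P(X ≥ 178) with X ~ Bin(355, c × S), where c is assumed completion among living patients and independent of survival. Ranges run from month-6 survival to window-opening survival, deaths only:

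| c | 60% one-year survival | 70% | 80% | no deaths |
|---|---|---|---|---|
| 55% | 0.3-1% | 7-13% | 38-47% | 97% |
| 60% | 9-21% | 53-68% | 92-95% | >99.9% |
| 65% | 55-76% | 95-98% | – | – |
| 70% | 94-99% | – | – | – |

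Mortality can decide the label when completion among living patients lies between about 50% and 65%. Above that range the rule is usually met.

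**Is the treatment of deaths open?** No. Section 7.2 fixes the numerator (baseline plus one follow-up form) and the denominator (eligible patients). Sections 10.2a and 10.3b rule out a form after the patient's death. Together they leave one reading: an early death stays in the denominator and out of the numerator.

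**Can the causes be separated?** Yes. Caregiver participation is recorded at registration (10.1d), deaths on the Off Protocol Notice (4.8), and the reason for each missing caregiver form on the Cover Sheet (10.3e).

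**Bereaved caregivers.** Sections 10.2a and 10.3b, the calendar and the submission schedule all agree that nothing is collected after the patient's death. No objective in 1.1 to 1.3 mentions bereavement. The phrase in 7.3 stands alone against them.

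**The case for a change.** The best argument for a change is consistency. Elsewhere the plan deals with mortality openly: cumulative incidence for the primary endpoint (7.1), a stated limitation for six-month quality of life (7.2), and repeated credit reports to limit bias from death (7.3). Only the caregiver rule is silent. With 60% completion among living patients, the rule would be met 9-21% of the time on the plan's survival and more than 99.9% of the time with no deaths, so the same caregiver behaviour could earn opposite labels. Choosing companion denominators after seeing the result is also weaker than naming them beforehand, and naming them would cost a few sentences.

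What stands is that a bare pass or fail would be hard to interpret, and that 7.2 does not commit to a breakdown. But the label itself cannot be moved after the fact, because its numerator and denominator are already written down. Figures restricted to surviving patients describe a selected group and could only accompany the all-eligible rate. Section 7.2 already refers to caregiver accrual as a separate quantity and plans proportions describing participating caregivers. Reporting reasons for missing forms is routine and uses data in hand.

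**Conclusion.** No change to the plan follows. The rule is an all-eligible yield, a fair test of whether a caregiver component delivers usable longitudinal data in this population, since early deaths are part of what a future study would face. It is demanding but attainable: more than half of eligible patients equals about 63-65% of living patients on the plan's survival, about 66-68% if all non-death dropout also ends caregiver participation, and about 55-60% if one-year mortality is 20-30%. These figures assume a constant hazard from registration, as the plan does. The pass probabilities also rest on assumed completion rates that are independent of survival.

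Little hangs on the label. No stated action follows from missing 50%, the only caregiver trigger with a consequence is accrual below 20%, and the primary estimate is untouched. What is missing is descriptive detail that analysts can supply sensibly: recruitment, completion among patients alive and on protocol, and reasons for missing forms, set beside the criterion.

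The bereaved-caregiver phrase in 7.3 is a real inconsistency with 10.2a and 10.3b, but an editorial one. It serves no objective, has no data to summarise, and removing or ignoring it changes no result.

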Given non-restrictive eligibility criteria, we anticipate a low rate of ineligibility (5%). In addition, 10% of patients are anticipated not to complete their baseline forms and will be inevaluable. Therefore 374 total patients will be enrolled to obtain 320 eligible, evaluable patients.

The total number of patients experiencing at least one financial hardship at each study interval will be determined. The proportion of patients experiencing multiple financial hardships will also be reported.

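### The caregiver financial-burden comparison asks about level of burden but tests only a cut at 3 on a Likert scale, giving up power that the full score would keep

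*Combined protocol and SAP*

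**What the plan says.** In the Feasibility part of Section 7.2, the caregiver paragraph gives its aim as the "association between patient-reported financial hardship and level of caregiver-reported financial burden". The test it names is a comparison of two groups of caregivers, "for patients who do vs. do not report major financial hardship using two-sample t tests". The outcome in that comparison is not the score itself but a share of caregivers above a cut: high financial burden is defined as 3 or more on a Likert scale. The section gives no number of scale points, reason for the cut, alpha or power for this comparison. It does not say whether the t test is pooled or unequal-variance.

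Three other statements set the scale and status of the analysis:

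- The paragraph says: "Our analyses will be largely descriptive".
- The caregiver component counts as feasible if the "designated caregivers for > 50% of eligible patients complete and submit their baseline" form and at least one follow-up form. The fallback is: "If our caregiver accrual is very poor (<20%), we will focus on describing the patient population". The comparison may therefore be run at any participation from 20% upwards.
- Section 7.3 says that the plan "will compare populations using two-sample means and proportions tests (α level 0.05"). It also compares mean Caregiver Strain Index (0 to 26), uncut, by patient hardship.

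**The concern.** The aim and the analysis do not match. Level of burden is an ordered quantity, but the named analysis only asks whether a caregiver is above or below one point on the scale. A caregiver who moves from 3 to 5, or from 1 to 2, contributes nothing. Caregiver participation is optional, so the sample may be small, and a small sample can least afford the loss.

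The outcome and the test do not match either. A proportion is paired with a test of means, although Section 7.3 distinguishes tests of means from tests of proportions. A programmer cannot tell whether the t test was meant for the mean Likert score or for the proportion.

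What is at stake is the chance of detecting an association in a secondary, exploratory comparison. The primary objective is not affected.

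**Working it through.** **No figure to reproduce.** The document states no power or effect size for this comparison. The base sample does reproduce: 320/(0.95 × 0.90) = 374.3, in line with "374 total patients will be enrolled to obtain 320 eligible, evaluable patients".

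**Inputs from the document**

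- Caregivers at the feasibility threshold: 50% × 320 = 160.
- Caregivers at the floor for running the comparison: 20% × 320 = 64.
- Hardship split: 40% anticipated (Section 7.1). This gives 64 vs 96 at the threshold and, rounding 25.6, 26 vs 38 at the floor.
- Alpha: 0.05 from Section 7.3, assumed to apply here and assumed two-sided.

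**Assumed, because the document does not give them:** the number of scale points, the score distribution, and a latent normal shift of 0.5 SD towards higher burden in the hardship group.

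**Step 1: one case by hand** (5 points, equally likely in the no-hardship group, 64 vs 96).

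- Cut: P(≥3) is 0.600 without hardship, so the latent threshold is −0.253. With hardship it is Φ(0.253 + 0.5) = 0.774. The pooled proportion is (64 × 0.774 + 96 × 0.600)/160 = 0.670.
- Null SE = √[0.670 × 0.330 × (1/64 + 1/96)] = 0.0759. Alternative SE = √[0.774 × 0.226/64 + 0.6 × 0.4/96] = 0.0723.
- Power = Φ[(0.174 − 1.96 × 0.0759)/0.0723] ≈ 64%.
- Full score: means 3.648 vs 3.000, variances 1.771 and 2.000. SE = √(1.771/64 + 2.000/96) = 0.220. Power ≈ Φ(0.648/0.220 − 1.96) ≈ 84% by normal approximation. Simulation gives 82.6%.

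**Step 2: simulated power over seven assumed distributions** (8,000 runs each; rank test on the full score / test on the ≥3 cut).

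| Scale, no-hardship group | P(≥3), no hardship | 64 vs 96 | 26 vs 38 |
|---|---|---|---|
| 5-point uniform | 60% | 82.6 / 63.7 | 42.8 / 31.0 |
| 5-point bell | 70% | 83.0 / 58.0 | 44.4 / 25.6 |
| 5-point skewed low | 30% | 81.0 / 67.6 | 43.7 / 33.7 |
| 5-point skewed high | 85% | 78.3 / 39.2 | 40.0 / 13.8 |
| 4-point uniform | 50% | 81.1 / 68.2 | 42.6 / 33.5 |
| 4-point skewed low | 25% | 80.6 / 66.7 | 42.0 / 32.5 |
| 0–4 uniform | 40% | 81.7 / 69.2 | 44.0 / 34.2 |

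Outside the skewed-high case the loss is 12.5 to 25 points at 64 vs 96 and about 9 to 19 points at 26 vs 38. Skewed high loses 39 and 26 points. A separate simulation on 5-point scales gave 57–69% against about 82%, and 28–33% against 43–45%.

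The asymptotic efficiency of the cut relative to the mean score is 0.63 to 0.74 (0.50 when skewed high). To match the full score, the cut would need 1/0.74 ≈ 1.35 to 1/0.63 ≈ 1.6 times as many caregivers, and 2 times in the extreme case.

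**Step 3: the t test on 0/1 data** (exact enumeration of all 2×2 tables, true proportion 5% to 50%, nominal 5%).

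| Type I error | 64 vs 96 | 26 vs 38 |
|---|---|---|
| Chi-square | 4.8–5.1% | 2.6–5.2% |
| Pooled t | 4.5–4.9% | 2.6–5.2% |
| Unequal-variance t | 4.9–5.6% | 3.8–5.6% |

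Pooled t and chi-square reach different decisions in 4 of 6,305 possible tables at 64 vs 96 and in 0 of 1,053 at 26 vs 38. For 50% vs 30% at 64 vs 96, power is 72.6% (chi-square), 72.6% (pooled t), 71.7% (unequal-variance t) and 69.2% (Fisher). Changing the test alone therefore gains nothing. The loss comes from the cut.

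**The case against.** The strongest reply is that this is an exploratory comparison, described as mostly descriptive, with no power claimed and serving a feasibility objective. A proportion with high burden is easy to read, and it answers the plan's expectation that caregivers of patients with hardship will more often report burden. The size of the loss rests on a scale, distribution and effect that the document does not give. All of this stands and limits the importance of the point. It does not remove the mismatch with the stated aim, and the cut lost power in every case tried. The paragraph also names a significance test, so the result is likely to be read as more than description.

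A reader might infer that the t test inflates the false-positive rate. The document does not support that. An exact error of 13.8% can be produced, but it needs the unequal-variance form, 10% high burden and a 16 vs 48 split, all together. The plan states none of these and anticipates 40:60. The same test gives 8.9% at 20 vs 44 with 10% high burden, so marked imbalance with uncommon high burden would be a weakness of that form. The pooled form at 16 vs 48 stays at 3.7–5.6%.

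A reader might also infer that this is the only caregiver comparison by patient hardship. It is the only test named for the financial-burden item, but Section 7.3 compares the Caregiver Strain Index without a cut. That index is a different measure and does not replace this one.

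**Conclusion.** The point holds as a minor one. Under a 5-point scale and a 0.5 SD latent shift, both assumed, the cut costs roughly 10–25 points of power at the caregiver numbers implied by the plan. It costs more if nearly all caregivers already score 3 or above. The model moves the whole scale together; if hardship acted only across the boundary between 2 and 3, the cut would lose little or nothing. The direction of the loss is therefore well founded for a general shift in level, which is what the aim describes, but its size cannot be fixed from the document. The t test named for a proportion should be tidied up as wording. It is not an error-rate problem at the anticipated split.

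**What to change.** In the caregiver paragraph of Section 7.2, make the comparison of the full Likert score between hardship groups the named analysis, by Wilcoxon rank-sum or by proportional-odds regression with the odds ratio and 95% CI. Keep the proportion scoring 3 or more as a descriptive summary. If that proportion is tested, name chi-square, or Fisher's exact test where expected counts are small, accepting slightly lower power (33.1% against 36.7% for 50% vs 30% at 26 vs 38). In the same edit, state the range of the scale and which caregiver assessment is analysed. The questionnaire is not reproduced in the document, so the range may already be clear there.

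The cost is an edit to one short passage. No new data are needed. The only downside is that an odds ratio or rank statistic has to be reported beside the proportion.
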